## ECOG-ACRIN Generic Specimen Submission Form Form No. 2981v3

**Institution Instructions:** This form is to be completed and submitted with **all specimens** ONLY if the Sample Tracking System (STS) is not available. **Use one form per patient, per time- point.** All specimens shipped to the laboratory must be listed on this form. Enter all dates as MM/DD/YY. Keep a copy for your files. Retroactively log all specimens into STS once the system is available. **Contact the receiving lab to inform them of shipments that will be sent with this form.**

Protocol Number \_\_\_\_\_

Patient ID \_\_\_\_\_

Patient Initials Last \_\_\_\_\_ First \_\_\_\_\_

Date Shipped \_\_\_\_\_

Courier \_\_\_\_\_

Courier Tracking Number \_\_\_\_\_

Shipped To (Laboratory Name) \_\_\_\_\_ Date CRA will log into STS \_\_\_\_\_

FORMS AND REPORTS: Include all forms and reports as directed per protocol, e.g., pathology, cytogenetics, flow cytometry, patient consult, etc.

Required fields for all samples			Additional fields for tissue submissions				Completed by Receiving Lab
Protocol Specified Timepoint:							
Sample Type (fluid or fresh tissue, include collection tube type)	Quantity	Collection Date and Time 24 HR	Surgical or Sample ID	Anatomic Site	Disease Status (e.g., primary, mets, normal)	Stain or Fixative	Lab ID

Fields to be completed if requested per protocol. Refer to the protocol-specific sample submissions for additional fields that may be required.					
Leukemia/Myeloma Studies:	Diagnosis	Intended Treatment Trial	Peripheral WBC Count (x1000)	Peripheral Blasts %	Lymphocytes %
Study Drug Information:	Therapy Drug Name	Date Drug Administered	Start Time 24 HR	Stop Time 24HR	
Caloric Intake:	Date of Last Caloric Intake		Time of Last Caloric Intake 24HR		

CRA Name \_\_\_\_\_ CRA Phone \_\_\_\_\_ CRA Email \_\_\_\_\_

Comments \_\_\_\_\_

9/12/14

**A Randomized Phase II Study of Temozolomide or Temozolomide and Capecitabine in  
Patients with Advanced Pancreatic Neuroendocrine Tumors**

**Appendix II**

**Patient Thank You Letter**

We ask that the physician use the template contained in this appendix to prepare a letter thanking the patient for enrolling in this trial. The template is intended as a guide and can be downloaded from the ECOG web site at <http://www.ecog.org>. As this is a personal letter, physicians may elect to further tailor the text to their situation.

This small gesture is a part of a broader program being undertaken by ECOG-ACRIN and the NCI to increase awareness of the importance of clinical trials and improve accrual and follow-through. We appreciate your help in this effort.

---

[PATIENT NAME]

[DATE]

[PATIENT ADDRESS]

Dear [PATIENT SALUTATION],

Thank you for agreeing to take part in this important research study. Many questions remain unanswered in cancer. With the help of people like you who participate in clinical trials, we will achieve our goal of effectively treating and ultimately curing cancer.

We believe you will receive high quality, complete care. I and my research staff will maintain very close contact with you. This will allow me to provide you with the best care while learning as much as possible to help you and other patients.

On behalf of **[INSTITUTION]** and the ECOG-ACRIN Cancer Research Group, we thank you again and look forward to helping you.

Sincerely,

[PHYSICIAN NAME]

**A Randomized Phase II Study of Temozolomide or Temozolomide and Capecitabine in  
Patients with Advanced Pancreatic Neuroendocrine Tumors**

**Appendix III**

**Patient Pill Calendar**

**Pill Calendar Directions**

1. Take your scheduled dose of each pill as instructed by your doctor.
2. If you forget to take the pills, the missed pills will not be taken later.
3. Complete the appropriate calendar based on the arm you are assigned to (Arm A or Arm B).
4. Note the number of pills you take each day. If you develop any side effects/symptoms, please record them in the appropriate spot on your calendar. If you take any medication other than temozolomide or capecitabine, note them in the appropriate spot on your calendar.
5. Do **not** take study medication on a day that has "XXXXX" on the calendar.
6. Please bring the empty bottle(s), any leftover pills and your pill calendar to your next clinic visit.

Rev. 7/15

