## 5. Treatment Plan

### 5.1 Administration Schedule

One cycle = 28 days

All doses are based on actual weight. If there is a  $< 5\%$  change in Body Surface Area (BSA), keep the doses the same. If there is a  $\geq 5\%$  change in BSA, a new dosing weight and BSA should be set and used for dose calculations.

- Temozolomide
  - The temozolomide dose will be capped at 400 mg daily. The calculated dose by BSA will be rounded down to minimize the number of capsules required. The treating investigator should use their best judgment to meet these guidelines.
  - Temozolomide should be taken by mouth at night after fasting from solid food for two hours. Temozolomide capsules must not be crushed and must be administered whole.
  - Temozolomide missed doses will not be made up and patients should not double-up on missed doses during treatment.
  - Ondansetron or other anti-emetic is strongly suggested as a premedication 30-60 minutes prior to temozolomide. Otherwise, anti-emetics, anxiolytics, and analgesics may be provided at physicians' discretion.
- Capecitabine
  - The calculated total daily capecitabine dose by BSA will be rounded down to allow doses using 500 mg tablets. Investigators should approximate the calculated dose based on the pill size available while rounding down to minimize the number of capsules required. The treating investigator should use their best judgment to meet these guidelines.
  - Capecitabine should be taken morning and night, with at least 8 hours between each dose. Capecitabine tablets should be swallowed with water within 30 minutes after a meal.
  - Capecitabine missed doses will not be made up and patients should not double-up on missed doses during treatment.

**NOTE:** Monitor CBC and platelet count prior to drug administration.

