#### 5.1.2 ARM B

Capecitabine 750 mg/m^2 po BID days 1-14

Temozolomide 200 mg/m^2 po QD days 10-14

Repeat cycles every 28 days

Maximum duration of treatment 13 cycles (approximately 1 year)

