8.2.5 Dose Specifics  
ARM A: None  
ARM B: 750 mg/m^2 po BID on days 1-14  
The calculated total daily dose by body surface area (BSA) will be rounded down to the nearest 500 mg allow doses using 500 mg tablets.

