**E2211 Patient Pill Calendar – Arm B**

	Patient ID: _____ Cycle #: _____ Dose: Take _____ # of Temozolomide capsules once daily Dose: Take _____ # of Capecitabine tablets twice daily					
Cycle Day	Date	Capecitabine	Times	Temozolomide	Time	Notes
	MM/DD/YY	# of Tablets Taken	XX:XX AM/PM	# of Capsules Taken	XX:XX PM	Note any symptoms/side effects you experience or any medications you take besides Capecitabine or Temozolomide.
1				XXXXXX	XXX	
2				XXXXXX	XXX	
3				XXXXXX	XXX	
4				XXXXXX	XXX	
5				XXXXXX	XXX	
6				XXXXXX	XXX	
7				XXXXXX	XXX	
8				XXXXXX	XXX	
9				XXXXXX	XXX	
10						
11						
12						
13						
14						
15		XXXXXX	XXXXXX	XXXXXX	XXXXXX	
16		XXXXXX	XXXXXX	XXXXXX	XXXXXX	
17		XXXXXX	XXXXXX	XXXXXX	XXXXXX	
18		XXXXXX	XXXXXX	XXXXXX	XXXXXX	
19		XXXXXX	XXXXXX	XXXXXX	XXXXXX	
20		XXXXXX	XXXXXX	XXXXXX	XXXXXX	
21		XXXXXX	XXXXXX	XXXXXX	XXXXXX	
22		XXXXXX	XXXXXX	XXXXXX	XXXXXX	
23		XXXXXX	XXXXXX	XXXXXX	XXXXXX	
24		XXXXXX	XXXXXX	XXXXXX	XXXXXX	
25		XXXXXX	XXXXXX	XXXXXX	XXXXXX	
26		XXXXXX	XXXXXX	XXXXXX	XXXXXX	
27		XXXXXX	XXXXXX	XXXXXX	XXXXXX	
28		XXXXXX	XXXXXX	XXXXXX	XXXXXX	

**A Randomized Phase II Study of Temozolomide or Temozolomide and Capecitabine in  
Patients with Advanced Pancreatic Neuroendocrine Tumors**

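### Pill-calendar direction 5 is worded by day, not by drug, so on the Arm B calendar it literally forbids capecitabine on days 1-9, contrary to section 5.1.2

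*Combined protocol and SAP*

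**What the plan says.** Appendix III gives one set of directions for both arms, followed by a separate calendar for each arm. Direction 5 instructs the patient not to "take study medication on a day that has 'XXXXX' on the calendar". No other direction explains what the X marks mean.

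The Arm A calendar covers temozolomide alone and marks days 6-28. The Arm B calendar has separate columns for capecitabine and temozolomide. On days 1-9 the temozolomide cells are crossed out and the capecitabine cells are open. On days 10-14 nothing is crossed out. On days 15-28 both drugs are crossed out. The Arm B header has a dose line for the number "of Capecitabine tablets twice daily", without cycle days.

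The capecitabine schedule is stated the same way in two places: "po BID days 1-14" in section 5.1.2 and "po BID on days 1-14" in section 8.2.5. Section 5.1.2 places Arm B temozolomide on days 10-14. Section 5.1 adds: "Capecitabine missed doses will not be made up and patients should not double-up on missed doses during treatment".

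Two other directions bear on the point. Direction 1 reads "Take your scheduled dose of each pill as instructed by your doctor". Direction 6 asks the patient to bring "any leftover pills and your pill calendar to your next clinic visit".

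**The concern.** A rule set by day is safe when the calendar holds one drug. On a two-drug calendar with different schedules, a day can be an off day for one drug and a dosing day for the other. Days 1-9 in Arm B are exactly that. Direction 5 applies to study medication as a whole, so a patient who follows it to the letter would take nothing on those days, although the protocol requires capecitabine.

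Any effect would fall on the experimental arm only and in one direction, towards less capecitabine, which is the drug whose addition the trial is testing. Skipped doses would be lost, because section 5.1 does not allow them to be made up and direction 2 tells patients the same.

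**Working it through.** The plan gives no figure on this point to reproduce. The check compares the calendar marks with the dosing schedule and counts days.

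**Inputs**

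| Item | Days | Source |
|---|---|---|
| Arm B capecitabine due, 750 mg/m² twice daily | 1-14 | 5.1.2, 8.2.5 |
| Arm B temozolomide due | 10-14 | 5.1.2, 8.1.5 |
| Arm A temozolomide due | 1-5 | 5.1.1, 8.1.5 |
| Arm B capecitabine columns crossed out | 15-28 | Appendix III, Arm B calendar |
| Arm B temozolomide columns crossed out | 1-9 and 15-28 | Appendix III, Arm B calendar |
| Arm A temozolomide columns crossed out | 6-28 | Appendix III, Arm A calendar |

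**Direction 5 as written (any X mark on the day bars all study medication)**

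- Arm B days with at least one X mark: 1-9 and 15-28. The only days on which medication is allowed are 10-14.
- Capecitabine: due on days 1-14, barred on days 1-9. That is 9 of 14 days, and 9/14 = 64.3%.
- Doses: 9 × 2 = 18 barred, out of 14 × 2 = 28.
- Amount: 750 × 2 = 1,500 mg/m² per day. Planned: 14 × 1,500 = 21,000 mg/m² per cycle. Under the literal reading: 5 × 1,500 = 7,500 mg/m². Lost: 13,500 mg/m² per cycle. These amounts are before rounding to 500 mg tablets.
- Arm B temozolomide: due on days 10-14, 0 of 5 days barred.
- Arm A temozolomide: due on days 1-5, marked on days 6-28, 0 of 5 days barred.

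**Does the number of X's separate the cases?** Direction 5 prints five X's, and the Arm B drug-count columns print six. If only a five-X mark counted, direction 5 would bar no day in Arm B, not even the true off days 15-28. If any X mark counts, capecitabine is wrongly barred on days 1-9. The temozolomide count column carries the same six-X mark on days 1-9 as both drugs carry on days 15-28, so the mark itself cannot tell the patient which days are fully off.

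**Rule by drug column (a drug is barred only where its own column is crossed out)**

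- Arm B capecitabine: marked on 15-28, due on 1-14, 0 of 14 days barred.
- Arm B temozolomide: marked on 1-9 and 15-28, due on 10-14, 0 of 5 days barred.
- Arm A temozolomide: marked on 6-28, due on 1-5, 0 of 5 days barred.

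This rule reproduces the protocol schedule in both arms and still bars every true off day.

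**The case against.** The strongest reply is that the handout largely resolves the ambiguity by itself. The marks sit in drug-specific columns. On days 1-9 the capecitabine cells are left open to be filled in, and the header has a separate capecitabine dose line. Direction 1 sends the patient back to the doctor's instructions for each pill. The literal reading would make nine rows of open capecitabine cells pointless and squeeze both drugs into days 10-14. On this view the sentence can be misread, but it hardly contradicts the schedule.

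The 64% is also a within-cycle figure for an unusual reader. Patients are assessed on day 1 of each cycle (section 7.1) and bring back their calendar and leftover pills. If the error came to light at the first return visit and the patient completed all 13 cycles, the loss would be 9 of 14 × 13 = 182 capecitabine days, about 5%. That share is larger if fewer cycles are given or detection is later.

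Most of this stands. The layout does point to the right reading, many patients would probably dose correctly, and the 64% should be read only as the one-cycle loss for a patient who follows the sentence literally. No bias in progression-free survival or response has been shown. However, none of these features qualifies direction 5. It is the only direction that interprets the X marks, and what it says is wrong for the Arm B grid. Detection at the next visit comes after that cycle's doses have been lost.

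**Conclusion.** The concern holds, as a minor one. Direction 5 as written conflicts with the capecitabine schedule on days 1-9 of every Arm B cycle. For a patient who follows it literally, the size is 9 of 14 capecitabine days (64%), or 18 of 28 doses, in each affected cycle. Temozolomide is untouched in both arms.

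The counts rest on two things: that any X mark on a day triggers the rule, and that the patient does not let the open cells, the dose line or the doctor's instruction override it. How many patients would do that is unknown, so the finding stops at the individual patient. The dosing schedule in the body of the protocol and the layout of the calendar agree with each other; the fault is in one patient-facing sentence. No statistical figure in section 9 depends on it.

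**What to change.** Reword direction 5 by drug, for example: *Do not take a drug on a day when that drug's own column shows X marks.* This is sufficient, and it works unchanged for both arms.

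A line on the Arm B calendar stating that X marks in one drug's column do not apply to the other drug would be a helpful reminder, but it is optional.

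The cost is one or two sentences in a handout, reissued with the next amendment. Section 5.1.2, the sample size and the analysis stay as they are.

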**E2211 Patient Pill Calendar – Arm A**

	Patient ID: _____ Dose: Take _____ # of capsules once daily	Cycle #: _____		
Cycle Day	Date	Temozolomide	Time	Notes
	MM/DD/YY	# of Capsules Taken	XX:XX PM	Note any symptoms/side effects you experience or any medications you take besides Temozolomide.
1				
2				
3				
4				
5				
6		XXXXX	XXXXX	
7		XXXXX	XXXXX	
8		XXXXX	XXXXX	
9		XXXXX	XXXXX	
10		XXXXX	XXXXX	
11		XXXXX	XXXXX	
12		XXXXX	XXXXX	
13		XXXXX	XXXXX	
14		XXXXX	XXXXX	
15		XXXXX	XXXXX	
16		XXXXX	XXXXX	
17		XXXXX	XXXXX	
18		XXXXX	XXXXX	
19		XXXXX	XXXXX	
20		XXXXX	XXXXX	
21		XXXXX	XXXXX	
22		XXXXX	XXXXX	
23		XXXXX	XXXXX	
24		XXXXX	XXXXX	
25		XXXXX	XXXXX	
26		XXXXX	XXXXX	
27		XXXXX	XXXXX	
28		XXXXX	XXXXX	

**E2211 Patient Pill Calendar – Arm B**

	Patient ID: _____ Cycle #: _____ Dose: Take _____ # of Temozolomide capsules once daily Dose: Take _____ # of Capecitabine tablets twice daily					
Cycle Day	Date	Capecitabine	Times	Temozolomide	Time	Notes
	MM/DD/YY	# of Tablets Taken	XX:XX AM/PM	# of Capsules Taken	XX:XX PM	Note any symptoms/side effects you experience or any medications you take besides Capecitabine or Temozolomide.
1				XXXXXX	XXX	
2				XXXXXX	XXX	
3				XXXXXX	XXX	
4				XXXXXX	XXX	
5				XXXXXX	XXX	
6				XXXXXX	XXX	
7				XXXXXX	XXX	
8				XXXXXX	XXX	
9				XXXXXX	XXX	
10						
11						
12						
13						
14						
15		XXXXXX	XXXXXX	XXXXXX	XXXXXX	
16		XXXXXX	XXXXXX	XXXXXX	XXXXXX	
17		XXXXXX	XXXXXX	XXXXXX	XXXXXX	
18		XXXXXX	XXXXXX	XXXXXX	XXXXXX	
19		XXXXXX	XXXXXX	XXXXXX	XXXXXX	
20		XXXXXX	XXXXXX	XXXXXX	XXXXXX	
21		XXXXXX	XXXXXX	XXXXXX	XXXXXX	
22		XXXXXX	XXXXXX	XXXXXX	XXXXXX	
23		XXXXXX	XXXXXX	XXXXXX	XXXXXX	
24		XXXXXX	XXXXXX	XXXXXX	XXXXXX	
25		XXXXXX	XXXXXX	XXXXXX	XXXXXX	
26		XXXXXX	XXXXXX	XXXXXX	XXXXXX	
27		XXXXXX	XXXXXX	XXXXXX	XXXXXX	
28		XXXXXX	XXXXXX	XXXXXX	XXXXXX	

**A Randomized Phase II Study of Temozolomide or Temozolomide and Capecitabine in  
Patients with Advanced Pancreatic Neuroendocrine Tumors**

**Appendix IV**

**ECOG Performance Status**

PS 0	Fully active, able to carry on all pre-disease performance without restriction
PS 1	Restricted in physically strenuous activity but ambulatory and able to carry out work of a light or sedentary nature e.g., light house work, office work.
PS 2	Ambulatory and capable of all self-care but unable to carry out any work activities. Up and about more than 50% of waking hours.
PS 3	Capable of only limited self-care, confined to bed or chair more than 50% of waking hours.
PS 4	Completely disabled. Cannot carry on any self-care. Totally confined to bed or chair.
